An adverse event (AE) is any untoward medical occurrence in a patient or clinical investigation subject administered a pharmaceutical product and which does not necessarily have to have a causal relationship with this treatment. Participants (or their parents) will be encouraged to report any significant unsolicited adverse events in an open-ended question format, e.g. "How are you (or your child) doing? Are you (or your child) having any medical or clinical problems? If so, please tell me about them."

An adverse event of special interest (AESI) includes the following:

- Allergic type reactions (including anaphylaxis, hives, or facial and limb swelling occurring within 7 days of a vaccination visit)
- Myocarditis or pericarditis occurring during the study period
- Multisystem inflammatory syndrome in children (MIS-C) during the study period

A serious adverse event (SAE) is defined as an AE that meets one of the following conditions:

- Results in death during the period of protocol-defined surveillance
- Is life-threatening (defined as immediate risk of death at the time of the event)
- Requires inpatient hospitalization or prolonged hospitalization during the period of protocol-defined surveillance (other than routine hospital admission for an elective medical procedure or surgery)
- Results in congenital anomaly or birth defect
- Results in a persistent or significant disability/incapacity
- Any other important medical event that may not result in death, be life threatening, or require hospitalization, may be considered an SAE when, based upon appropriate medical judgment, the event may jeopardize the subject and may require medical or surgical intervention to prevent one of the outcomes listed above. Examples of such medical events include allergic bronchospasm requiring intensive treatment in an emergency room or at home, blood dyscrasias or convulsions that do not result in inpatient hospitalization, or the development of drug dependency or drug abuse.

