Unsolicited adverse events, AESIs and SAEs will be graded as described in **Table 6**. Participants who report severe solicited adverse events or express any concern about symptoms/unsolicited events will be encouraged to follow up with their primary care provider. Study staff will assist with coordination of referral appointments as necessary. Parent/LAR will be asked to agree to the release of information to obtain and review medical records for any unscheduled medical appointments, including clinic visits and telehealth visits, through 29 days after the second dose. Frequency and occurrence of serious AEs (SAEs), AESIs and unscheduled medical care for COVID-19 illness will be assessed through 181 days after dose 2 or a booster dose.

Table 4: Injection-site Reactogenicity			
Symptom	Mild (Grade 1)	Moderate (Grade 2)	Severe (Grade 3)
Pain	Does not interfere with activity	Interferes with activity	Prevents daily activity
Tenderness	Does not interfere with activity	Interferes with activity	Prevents daily activity
Underarm or groin swelling on same side as vaccine	Does not interfere with activity	Interferes with activity	Prevents daily activity
Swelling	5-11 years: 5-20 mm	5-11 years: 21-70 mm	5-11 years: >70 mm
	12 years >: 20-50 mm	12 years >: 51 - 100 mm	12 years: >100 mm
Redness	5-11 years: 5-20 mm	5-11 years: 21-70 mm	5-11 years: >70 mm
	12 years >: 20-50 mm	12 years >: 51 - 100 mm	12 years: >100 mm

Table 5: Systemic Reactogenicity			
Systemic	Mild (Grade 1)	Moderate (Grade 2)	Severe (Grade 3)
Fever (°C)	≥ 38.0 – 38.4 ≥ 100.4 - < 101.1° F	>38.4 – 38.9 ≥ 101.1 - < 102° F	> 38.9° C ≥ 102° F

Table 5: Systemic Reactogenicity			
Feverishness	Does not interfere with activity	Some interference with activity	Prevents daily routine activity
Chills	Does not interfere with activity	Some interference with activity	Prevents daily routine activity
Headache	Does not interfere with activity	Some interference with activity	Prevents daily routine activity
Fatigue	Does not interfere with activity	Some interference with activity	Prevents daily routine activity
Muscle Pain	Does not interfere with activity	Some interference with activity	Prevents daily routine activity
Joint Pain	Does not interfere with activity	Some interference with activity	Prevents daily routine activity
Vomiting	Does not interfere with activity	Some interference with activity	Prevents daily routine activity

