Diarrhea	Does not interfere with activity	Some interference with activity	Prevents daily routine activity
Nausea	Does not interfere with activity	Some interference with activity	Prevents daily routine activity
Facial or lip swelling	Does not interfere with activity	Some interference with activity	Prevents daily routine activity

Table 6: Grading for Unsolicited Adverse Events, AESIs and SAEs			
Mild (Grade 1)	Moderate (Grade 2)	Severe (Grade 3)	
Does not interfere with activity	Some interference with activity	Prevents daily routine activity	

In this study, COVID-19 vaccination is not a study procedure. COVID-19 vaccine administration will be given per standard of care to children and adolescents receiving vaccine under an EUA by the Food and Drug Administration. Published studies in children and adolescents found no vaccine-related serious adverse events in children or adolescents receiving BNT162b2 (3-5). Lymphadenopathy was identified as an adverse event occurring more frequently in BNT162b2 vs. placebo groups during clinical trials (11). Post-authorization vaccine safety data have identified two safety concerns that rarely can occur after vaccination: severe allergic reactions, including anaphylaxis, and myocarditis and pericarditis (11). Therefore, we do not anticipate any significant issue with serious adverse events (SAEs). Nevertheless, we will monitor study participants for SAEs during the protocol-defined surveillance period of 6 months after second dose or a booster dose. SAEs will be reported to the CDC and all participating IRBs according to institutional requirements.

Perceptions of COVID-19 vaccine

At Day 7 (+3) following each of the vaccination visits we will assess adolescent (ages 12 to < 16) and parent/LAR perceptions of the COVID-19 vaccine recommendations and experience with receipt of the vaccine. Questions are provided in **Tables 7 and 8** below. We will use a Likert scale (strongly agree, agree, neither, disagree, strongly disagree) to assess response to the questions about concerns regarding COVID-19 vaccine safety. As noted, adolescent and parent perceptions regarding vaccine receipt will be assessed at the reactogenicity assessment visits after each vaccine.

Table 7 Parental /LAR Perceptions of COVID-19 Vaccine Recommendations and Receipt

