Study site investigators will assess relatedness to COVID-19 vaccine or study procedures (related, possibly related, unlikely related, or not related) for SAEs and AESIs. Solicited symptoms in **Tables 4 and 5** will all be considered to be related to COVID-19 vaccine and causality assessment will not be done for these events. The study investigators will use their clinical judgement to make causality assessments and may consult the Safety Review Panel or CISA Project for assistance with causality determinations. The final causality assessment decision is the responsibility of the site PI where the subject was enrolled.

Reporting Adverse Events

SAEs and unanticipated problems will be reported to the CDC and all participating IRBs according to institutional requirements. Vaccination is not a study procedure.

Adverse events that occur in a recipient following COVID-19 vaccination should be reported to CDC's Vaccine Adverse Event Reporting System (VAERS). Vaccination providers are required by the Food and Drug Administration to report the following that occur after COVID-19 vaccination under Emergency Use Authorization:

- Vaccine administration errors
- Serious adverse events
- Cases of Multisystem Inflammatory Syndrome
- Cases of COVID-19 that result in hospitalization or death

Reporting is encouraged for any other clinically significant adverse event even if it is uncertain whether the vaccine caused the event. Information on how to submit a report to VAERS is available at <https://vaers.hhs.gov> or by calling [name].

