7.2.2 Primary Objective

Primary Objective – To characterize the safety of authorized and recommended COVID-19 vaccines among children and adolescent participants

1) Tables will be produced that summarize each solicited local and systemic reactogenicity event by maximum classification (none, mild, moderate, and severe), as well as by moderate or severe through days 1-7 following COVID-19 vaccination for dose 1 and dose 2 or a booster dose. These tables will have the number and percentage for each classification and will be broken down by each site and across all sites. In addition, the number and percentage of participants with at least one moderate-to-severe local or systemic reactogenicity event will be described, as well as the proportion of participants with at least one severe local or systemic reactogenicity event. (POM 1, POM 2 and POM 3)

2) Tables will be produced that summarize each unsolicited adverse event by maximum classification (none, mild, moderate, and severe), as well as by moderate or severe through days 1-7 following COVID-19 vaccination for dose 1 and dose 2 or a booster dose. These tables will have the number and percentage for each classification and will be broken down by each site and across all sites (POM4).

3) Tables will be produced that summarize participants experiencing at least one serious adverse event or one AESI through the 29 days after dose 2 or a booster dose. This table will have the number and percentage for each outcome. Listings with the clinical narratives will also be provided. (POM5 and POM6)

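### Does it matter that section 5.5 does not say which causality rule applies when a solicited symptom is also an SAE or AESI?

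*Combined protocol and SAP*

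**What the plan says.** Under the causality heading in section 5.5, two consecutive sentences set two rules.

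- **Assessed events.** "Study site investigators will assess relatedness to COVID-19 vaccine or study procedures", on a four-level scale: "related, possibly related, unlikely related, or not related) for SAEs and AESIs". No exception is made for events that are also solicited symptoms.
- **Events related by default.** The symptoms listed in the two reactogenicity tables (4 and 5) are treated differently: they "will all be considered to be related to COVID-19 vaccine and causality assessment will not be done for these events". No exception is made for events that are also serious or of special interest.

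The same paragraph gives the final causality decision to the principal investigator at the enrolling site, who may consult the safety panel or the CISA Project.

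The definitions that create the overlap are also in section 5.5. Allergic-type AESIs are described as "including anaphylaxis, hives, or facial and limb swelling occurring within 7 days of a vaccination visit", and Table 5 solicits "Facial or lip swelling". One SAE criterion reads "Requires inpatient hospitalization or prolonged hospitalization during the period of protocol-defined surveillance".

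On grading, section 5.5 says: "Unsolicited adverse events, AESIs and SAEs will be graded as described in" Table 6. Solicited symptoms have their own grading in Tables 4 and 5.

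**The concern.** Each sentence is written without qualification, and the two sets of events intersect. Read literally, an event in both sets must be assessed for relatedness and must also not be assessed. If the second sentence won, a serious or special-interest event would be labelled vaccine-related with no causality judgement on record, in a study whose primary objective is to characterise safety.

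The label would also be least reliable where it matters most. Some participants receive other vaccines at the same visit, and COVID-19 diagnoses are recorded during the diary week. Facial swelling after several vaccines, or admission with fever during an infection, would be attributed to the COVID-19 vaccine by default.

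**Working it through.** The plan gives no figure to reproduce, because the point concerns two text rules. The check has three steps.

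**1. Is there an overlap?**

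| Source (section 5.5) | Events covered | Window |
|---|---|---|
| Tables 4 and 5 | 5 local symptoms (pain, tenderness, underarm or groin swelling, swelling, redness) and 11 systemic symptoms (fever, feverishness, chills, headache, fatigue, muscle pain, joint pain, vomiting, diarrhea, nausea, facial or lip swelling); 5 + 11 = 16 | Days 1-7 |
| AESI definition, allergic type | Examples include facial swelling | 7 days from a vaccination visit |
| SAE definition | Any event meeting a seriousness criterion | Surveillance period |

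Yes. Facial swelling is named in both places, in nearly the same window. SAE status depends on outcome, so any of the 16 symptoms could become an SAE, for example through admission. The figure 16 measures the reach of the default rule, not the number of events affected.

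**2. Does the document settle which rule applies?**

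Not expressly, but it points one way:

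- Grading: solicited symptoms use Tables 4 and 5; AESIs and SAEs use Table 6 with unsolicited events. This governs grading only, yet it shows that AESIs and SAEs are handled as their own class.
- Causality: the two sentences follow the same split.
- Review: section 7.2.5 sends SAE and AESI narratives to a panel of non-investigators.
- Recognition: deciding that a diary entry of facial swelling is an allergic-type reaction already takes clinical judgement.

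On this reading, once an event is recorded as an AESI or SAE, the assessment sentence governs. The default sentence covers ordinary reactogenicity.

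**3. What depends on the answer?**

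| Item | Uses relatedness? |
|---|---|
| POM 5 and POM 6 (section 2) | No; numerators change by 0 |
| EOM 3 and EOM 4 (section 2) | No |
| Table sets, section 7.2.2 | 0 of 3 |
| Table sets, section 7.2.3 | 0 of 3 |
| Exact Mantel-Haenszel comparison, section 7.2.3 | No; it compares proportions with an event |
| Reporting of SAEs to the CDC and IRBs, section 5.5 | No condition stated; follows institutional requirements |
| VAERS reporting, section 5.5 | No; encouraged even where causation is uncertain |

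Table sets using relatedness: 0 + 0 = 0 of 3 + 3 = 6. For SAEs and AESIs, section 7.2.2 adds: "Listings with the clinical narratives will also be provided". A reader can therefore form a view of each case whatever label it carries.

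**The case for a change.** The strongest case for a change runs as follows. The overlap is real and no sentence resolves it. The default rule, taken literally, splits one AESI category: anaphylaxis and hives are not Table 4 or 5 items and would be assessed, while facial swelling in the same definition would not. Four sites make their own final decisions and could label the same event differently. Consulting the panel on causality is optional, so its narrative review does not guarantee a consistent label. The remedy is one clause.

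Most of the factual part stands: the overlap exists, precedence is unstated, and labels could differ between sites. The other safeguards are also partial. The prompted call concerns new rash, and telephone follow-up in the web-diary instructions is triggered by missing values, hives or Grade 3 events, so mild facial swelling need not trigger either.

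What does not stand is the step from there to a fault in the plan. The split arises only if the default sentence is read as overriding the one before it, against the arrangement of the rest of section 5.5. A difference in labels between sites would reach no estimate, comparison or planned table. The low cost of a clause is no reason to require it when nothing planned changes.

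**Conclusion.** No change to the plan is needed. This is a missing clarification that investigators would supply sensibly: an event recorded as an SAE or AESI is assessed for relatedness, and routine solicited reactions are taken as related. Treating solicited reactions as related by default is a choice the protocol states openly.

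The effect on results is nil: 0 change in POM 5 and POM 6, and 0 of 6 planned table sets affected. At most, the relatedness recorded for some SAEs or AESIs could differ. How many cannot be computed, because the documents give no rate for facial swelling or for admission with a solicited symptom; that they are few is a judgement.

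The conclusion rests on two assumptions. First, relatedness stays out of the analyses, including the separate statistical analysis plan to which section 7 defers further detail. Second, institutional reporting requirements, which the protocol follows but does not reproduce, do not turn on this label for the overlapping events. If either failed, stating the precedence would become worthwhile. As the plan stands, a sentence to that effect would be editorial.

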6 LABORATORY ANALYSES

Serum samples will be analyzed by the use of a qualitative enzyme-linked immunosorbent assay (ELISA) which measures IgG antibody to the SARS-CoV-2 Spike protein. Recombinant full length Spike protein is used to coat ELISA plates and serum samples that have an Optical Density (OD) value above the established cut off are considered positive for antibody. The assay was qualified for use in the Laboratory for Specialized Clinical Services at Cincinnati Children's Hospital Medical Center (CCHMC), a laboratory that is certified by the Clinical Laboratory Improvement Amendments (CLIA) and College of American Pathologist (CAP) under US FDA Emergency Use Authorization.

Qualitative serologic testing will be completed in periodic batches throughout the course of the study and will therefore not be available in real-time or for use in clinical decision-making. CCHMC will share participant results with submitting study sites as permitted by CDC. Study sites may share results with participants as permitted by FDA, CDC, and local site regulations.

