EOM 1: Proportion of participants and legal guardians/parents with negative or positive perceptions of the vaccination experience based on participants responses to individual questions on the perceptions questionnaire

EOM 2: Assessment of primary outcome measures 1-6 in those with positive baseline COVID-19 serostatus versus those with a negative baseline serostatus

EOM 3: Proportion of participants with an adverse event of special interest through 6 months after dose 2 of COVID-19 vaccine or a booster dose

EOM 4: Proportion of participants with a serious adverse event through 6 months after dose 2 of COVID-19 vaccine or a booster dose

EOM 5a: The proportion of participants seropositive to SARS-CoV-2 variants tested prior to and following mRNA COVID-19 vaccine in a subset of children and adolescents

EOM 5b: The geometric mean ID₅₀ and ID₈₀ titers of neutralizing antibodies for each SARS-CoV-2 variant tested pre- and post-mRNA COVID-19 vaccine in a subset of child and adolescent participants.

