3.2 Laboratory studies

3.2.1 Serologic studies

We will evaluate pre-serologic responses at three sites using an opt-in strategy. Prevaccination blood samples will be analyzed qualitatively for COVID-19 (SARS-CoV-2) antibody status (positive or negative) at Cincinnati Children's Hospital Medical Center in a CLIA-certified lab. Venous blood (approximately 5 mL of blood) will be collected from each participant in close proximity to the first vaccination (up to 3 days before or after vaccination). Venous blood will also be collected approximately 28 days after the second dose of vaccine received and stored for COVID-19 vaccine immunogenicity studies.

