3.2.2 SARS-CoV-2 Antibody Assay

For children and adolescents at participating sites, optional blood draws will occur on Day 1 (before vaccination) and 28 (+7) days after dose 2 or a booster dose to be stored for serum COVID-19 neutralization assays. COVID-19 neutralizing antibody titers will be assessed for each variant tested. Participants will not receive individual COVID-19 antibody titer results; these are not routinely used in clinical practice.

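### Baseline serostatus may reach sites and families before the dose 2 diary is complete, which could bias the exploratory serostatus comparison (EOM 2) at dose 2

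*Combined protocol and SAP*

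**What the plan says.** EOM 2 (section 2) is defined as "Assessment of primary outcome measures 1-6 in those with positive baseline COVID-19 serostatus versus those with a negative baseline serostatus". The baseline sample is taken within 3 days either side of the first vaccination (section 3.2.1), on an opt-in basis at three sites, Columbia excluded (section 5.4.2).

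Section 6 sets the timing and release of the positive/negative result:

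- On timing: "Qualitative serologic testing will be completed in periodic batches throughout the course of the study". The section adds that, for this reason, nobody will have a result immediately and none is meant to guide care.
- On release to sites: the Cincinnati laboratory passes individual results back to whichever site sent the sample, if CDC allows it.
- On release to families: "Study sites may share results with participants as permitted by FDA, CDC, and local site regulations".

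Section 3.2.2 contains the only bar on returning results: "Participants will not receive individual COVID-19 antibody titer results". It concerns the neutralization assay, not the ELISA status.

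Reactions are entered in the memory aid by the parent or participant on Days 1-7 after each dose (section 5.1, Tables 1 and 2). Apart from fever, swelling and redness, the symptoms in Tables 4 and 5 are graded by how far they interfere with activity. Staff telephone families using the electronic diary about missing values, hives or Grade 3 events (section 5.1). A new rash prompts a call to judge its severity and whether it is allergic (section 5.5).

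**The concern.** The person who reports the outcome may learn the exposure being compared before reporting is finished. A parent told that the child is antibody positive may look for, notice or grade symptoms differently. The Background supplies an expectation: it suggests that children with earlier symptomatic infection may react more strongly, as adults have. Staff who hold the result may likewise probe a rash, hives or a Grade 3 report differently. Allergic-type reactions within 7 days are AESIs and count in POM 5, so this follow-up can also enter EOM 2.

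Because release depends partly on local site regulations, the share told could differ by site. The plan does not ask for the date of disclosure to be recorded. A dose 2 difference by serostatus could then not be separated from a reporting effect, and a later analysis plan could not recover the missing information.

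**Working it through.** The documents give no figure on this point to reproduce. The check is a reading of the release rules, a timing calculation and a scaling of the possible shift.

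**Release rules.** Both release sentences in section 6 carry permission conditions (CDC; FDA, CDC and local rules) and no timing condition. The remark that results are not real-time describes what batching does and sets no hold. No section gives a batch interval or turnaround, or masks families or staff to serostatus.

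**Who is exposed.** Section 4.3 plans about 60 at Duke, 100 at Cincinnati and 90 at Kaiser: 60 + 100 + 90 = 250. Those who do not opt in and those enrolled at a booster come off this figure, so fewer than 250 are exposed. The documents do not give the split.

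**When the diary closes.** The Background reports trial dose intervals of 3 weeks (Pfizer) and 4 weeks (Moderna); in this study dose 2 follows standard of care. With vaccination as Day 1, Day 7 is 6 days later: 21 + 6 = 27 and 28 + 6 = 34 days after dose 1.

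**Share of results back in time.** Let T be the turnaround and B the batch interval, both assumed, with the delay from draw to result uniform on (T, T + B). For a draw on the day of dose 1, the share back by day d is (d − T)/B, limited to 0 to 1. Take T = 7 or 14 days and d = 27 or 34. The lowest value is (27 − 14)/B = 13/B and the highest is (34 − 7)/B = 27/B.

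**Possible shift.** If knowing the result changes reporting by δ in one serostatus group and a share s of that group is told in time, the EOM 2 difference moves by δ × s. Take δ = 5 to 10 percentage points, as an assumption. A result that is back has not necessarily been disclosed, so the table uses the largest s that the timing allows.

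| Assumed B (days) | Share back before dose 2 diary ends | Largest shift (points) |
|---|---|---|
| 14 | 93-100% | 4.6-10 |
| 30 | 43-90% | 2.2-9.0 |
| 60 | 22-45% | 1.1-4.5 |
| 90 | 14-30% | 0.7-3.0 |
| 180 | 7-15% | 0.4-1.5 |

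Example for B = 30: 13/30 = 0.43 and 27/30 = 0.90; 0.43 × 5 = 2.2 and 0.90 × 10 = 9.0.

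**Dose 1 and booster diaries.** Here d = 6, so the share is 0 for any T of 7 days or more. A draw 3 days before vaccination gives d = 9, and at T = 7 and B = 30 a share of 2/30 = 7%; at T = 14 it is 0.

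**Precision, for scale.** In the most favourable case, with all 250 children opted in, all first-dose enrollees and split 125/125, the 95% half-width for a difference between proportions near 50% is 1.96 × √(0.25/125 + 0.25/125) = 0.124, about 12 points.

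**The case against.** The case against has several parts.

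- **Early knowledge may be uncommon.** Results are batched, serum is frozen at the sites for later shipment (section 5.4.2), and release needs CDC permission and then a site's choice. This stands. It lowers the share told but sets no limit on it.
- **Families already know of diagnosed COVID-19.** Disease history is taken at Visit 1 and updated afterwards. This stands too: the result is new mainly where infection went undiagnosed, so a hold removes only part of any bias.
- **EOM 2 is exploratory.** It is opt-in, in an unrandomized descriptive study, and its analysis is left to a later analysis plan. That limits the importance of the point but does not answer it, because later analysis cannot undo unmasked reporting.
- **Returning results is a considered policy.** A hold delays it without withdrawing it.

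A reader might infer that investigators' relatedness judgements carry the bias, since "Study site investigators will assess relatedness to COVID-19 vaccine or study procedures". The documents do not support this. POM 5 and POM 6 count participants with any AESI or SAE, solicited symptoms are all taken as related, and relatedness enters none of POM 1-6. A reader might also infer that the full 5 to 10 points would pass into EOM 2. That requires everyone in the affected group to be told before reporting.

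**Conclusion.** The gap is real and small. Section 6 permits individual serostatus to be known before or during the self-reported dose 2 diary, and before staff follow up rash, hives or Grade 3 reports, for fewer than 250 first-dose enrollees. This could bias EOM 2 at dose 2.

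The size cannot be taken from the documents. It is an assumed reporting effect times an unknown share told in time. Under the assumptions above, the upper bound runs from under 2 points with long batch intervals to nearly the full assumed effect with two-week batches. The direction is also unknown.

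Three stronger readings are not supported. The protocol does not say that results will be disclosed early; it only leaves this possible. Nothing shows that such a shift would pass for a new safety signal: even the most favourable precision is about ±12 points, no EOM 2 test is specified here, and the Background itself raises the possibility of stronger reactions after symptomatic infection. The primary and secondary objectives do not use serostatus, and dose 1 and booster diaries normally close before a batched result could return. This is an inexpensive improvement to an exploratory comparison and not a flaw in the main aims.

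**What to change.** In section 6, state that a participant's baseline serostatus is not released to site staff or to the participant until the earliest of:

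- collection of that participant's last Days 1-7 memory aid (Visit 2a for the primary series, Visit 1a for a booster);
- withdrawal from the study;
- confirmation that no dose 2 will be received within the study.

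The last two are needed because dose 2 is not a study procedure, and some children will never reach Visit 2a.

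Record the release date for each participant, and the date of disclosure to the family where it differs. In the analysis plan for EOM 2 at dose 2, add a sensitivity analysis that excludes participants whose result was released before their diary was collected. If the hold is judged impractical, recording the dates alone would still allow that analysis.

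Batch testing can continue as planned. The cost is that some families receive a few weeks later a result that section 6 already describes as neither real-time nor for clinical decisions, and that the laboratory or data centre must track a release date per participant. The hold will reduce the bias but not remove it.
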